3.6.	Subjective Acceptance	Record whether the subject's distance and near vision with the lenses is acceptable.	
3.7.	Entrance Distance and Near Visual Acuity	Record the distance and near Snellen visual acuity (OD, OS, OU) to the nearest letter with the study contact lenses in place. For near measurements use the ETDRS 2000 Series Chart 1 or 2.	
3.8.	Binocular Distance Over-refraction and Distance Visual Acuity	Perform a binocular over-refraction and record the OD and OS results and distance visual acuity. Note: No lens changes are allowed based on the over-refraction.	Appendix F
3.9.	Toric Fit Evaluation	After lens settling, record: 
• The rotational position to the nearest degree• Lens stability with blink• Toric fit acceptable or unacceptable Toric lens fit will be unacceptable if lenses rotated more than 30 degrees, or lens stability is worse than 5 degrees movement with blink. If toric fit is unacceptable, remove, store, and label the lenses, and proceed to final evaluation.	
3.10.	Lens Fit Assessment	Evaluate and grade lens centration, primary gaze movement, upgaze movement and tightness (push-up test). 
• The subject should not proceed to wear the lenses if any of the following is observed:	

Clinical Study Protocol
Johnson & Johnson Vision Care, Inc.

Visit 3: Treatment 1 Follow-Up 2			
Step	Procedure	Details	
		
 • presence of limbal exposure (appearance of clear cornea) in any gaze • presence of edge lift • presence of unacceptable movement (excessive or insufficient) in all three movement categories (primary gaze, upgaze, and push-up). 
If either lens is deemed unacceptable, the subject will be discontinued from the study. Remove the lenses, perform a slit-lamp evaluation, and complete the Final Evaluation form.
	
3.11.	Visual Performance Distance (4 M) Intermediate (64 cm) Near (40 cm)	
Visual performance will be recorded OD, OS, and OU for the following:
 
Distance, Bright Illuminance ETDRS Charts 4 M-HC#1, HC#2, HC#3 and LC#1, LC#2 and LC#3
 
Near, Bright Illuminance Reduced Guillon-Poling Charts High Contrast and Low Contrast Intermediate (64 cm) and Near (40 cm).
 
Distance, Dim Illuminance (with Distance goggles) ETDRS Charts 4 M-HC#4, HC#5, HC#6
 
Near, Dim Illuminance (with Near goggles) Reduced Guillon-Poling charts High Contrast Intermediate (64 cm) and Near (40 cm).
 
Note:
 
 • The room illuminance must be between 7.3 and 7.9 EV (or 400 to 600 lux) • Distance, HC-1 Chart luminance Acceptable EV Range 10.5-10.7 (or 180 to 210 cd/m²) • Guillon-Poling, Near Chart Luminance Acceptable EV Range 10.8-11.1 (or 220 to 280 cd/m²) 	  

Clinical Study Protocol
Johnson & Johnson Vision Care, Inc.

Visit 3: Treatment 1 Follow-Up 2			
Step	Procedure	Details	
		
 • Do not use the Mesopic filter for Dim luminance (Dim luminance will be simulated by using the goggles). 	
3.12.	Lens Removal	Have the subject remove the study lenses and temporarily store them in a lens case with Biotrue® multipurpose solution.	
3.13.	Biomicroscopy	
FDA Slit Lamp Classification Scale will be used to grade the findings and determine eligibility.
 
If the clearance of the fluorescein needs to be expedited, preservative-free rewetting drops or saline may be instilled.
	
3.14.	Insertion of Study Lenses	Have the subject re-insert the lenses which had been removed at step 3.12.	
3.15.	Exit Distance and Near Visual Acuity	
Record the distance and near Snellen visual acuity (OD, OS, OU) to the nearest letter with the study contact lenses in place.
 
For near measurements use the ETDRS 2000 Series Chart 1 or 2.
	
3.16.	Subject Instructions	
Instruct the Subject on the following:
 
 • The lenses will be worn on a daily wear basis. • After each lens removal, use a rub/rinse/soak lens care regimen with Biotrue® multipurpose solution (per manufacturer's instructions). • If determined necessary by the Investigator sterile non-preserved rewetting drops may be dispensed to be used as needed for dryness. • Subjects will be instructed to wear lenses for a minimum of 6 hours a day, every day during the study. One missed day of lens wear per week is acceptable. • Subjects will be instructed to wear their glasses when not wearing the study lenses. • Subjects will be instructed to bring their habitual contacts or spectacles to the next visit. 	

Clinical Study Protocol
Johnson & Johnson Vision Care, Inc.

Visit 3: Treatment 1 Follow-Up 2			
Step	Procedure	Details	
		
Note: In the event a lens is lost or damaged after Visit 3, the subject will return to the investigator site for discontinuation and Final Evaluation. As much as reasonably possible, a damaged lens should be returned to the investigational site and then returned to the Sponsor. If lens damage is present, complete the Product Quality Complaint Form. The lens will be stored in labeled vial with Biotrue® multipurpose solution and returned to the Sponsor.
	
3.17.	Schedule Follow-up	The subject will be scheduled to return for their follow-up appointment which should be 25 to 31 days after Visit 2.	

VISIT 4

The subjects must present to Visit 4 wearing the study lenses.

Visit 4: Treatment 1 Follow-Up 3			
Step	Procedure	Details	
4.1.	Adverse Events and Concomitant Medications Review	Review any changes to the subject's medical history or concomitant medications from the previous study visit. Record any changes, and any adverse events.	
4.2.	Wear time and Comfortable Wear time (Study Lenses)	Record the average wearing time and comfortable wearing time with the study lenses.	
4.3.	Compliance	Confirm compliance with the prescribed wear schedule.	
4.4.	PRO (CLUE and MRD) and CLDEQ-8 Questionnaires	The subject will respond to the Follow-Up PRO (CLUE and MRD) and Dry Eye Questionnaires.	
4.5.	Subject Reported Ocular Symptoms	Subjects will respond to a verbal open-ended symptoms questionnaire.	
4.6.	Subjective Acceptance	Record whether the subject's distance and near vision with the lenses is acceptable.	
4.7.	Entrance Distance and Near Visual Acuity	Record the distance and near Snellen visual acuity (OD, OS, OU) to the nearest letter with the study contact lenses in place. For near measurements use the ETDRS 2000 Series Chart 1 or 2.	

Clinical Study Protocol
Johnson & Johnson Vision Care, Inc.

Visit 4: Treatment 1 Follow-Up 3			
Step	Procedure	Details	
4.8.	Binocular Distance Over-refraction and Distance Visual Acuity	
Perform a binocular over-refraction and record the OD and OS results and distance visual acuity.
 
Note: No lens changes are allowed based on the over-refraction.
	Appendix F
4.9.	Toric Fit Evaluation	
After lens settling, record:
 
 • The rotational position to the nearest degree • Lens stability with blink • Toric fit acceptable or unacceptable 
Toric lens fit will be unacceptable if lenses rotated more than 30 degrees, or lens stability is worse than 5 degrees movement with blink. If toric fit is unacceptable, remove, store, and label the lenses, and proceed to final evaluation.
	
4.10.	Lens Fit Assessment	
Evaluate and grade lens centration, primary gaze movement, upgaze movement and tightness (push-up test).
 
 • The subject should not proceed to wear the lenses if any of the following is observed: • presence of limbal exposure (appearance of clear cornea) in any gaze • presence of edge lift • presence of unacceptable movement (excessive or insufficient) in all three movement categories (primary gaze, upgaze, and push-up). 
If either lens is deemed unacceptable, the subject will be discontinued from the study. Remove the lenses, perform a slit-lamp evaluation, and complete the Final Evaluation form.
	
4.11.	Visual Performance Distance (4M) Intermediate (64 cm) Near (40 cm)	
Visual performance will be recorded OD, OS, and OU for the following:
 
Distance, Bright Illuminance
 
ETDRS Charts 4M-HC#1, HC#2, HC#3 and LC#1, LC#2 and LC#3
	

Clinical Study Protocol
Johnson & Johnson Vision Care, Inc.

Visit 4: Treatment 1 Follow-Up 3			
Step	Procedure	Details	
		
Near, Bright Illuminance Reduced Guillon-Poling Charts High Contrast and Low Contrast Intermediate (64 cm) and Near (40 cm).
 
Distance, Dim Illuminance (with Distance goggles) ETDRS Charts 4M-HC#4, HC#5, HC#6
 
Near, Dim Illuminance (with Near goggles) Reduced Guillon-Poling charts High Contrast Intermediate (64 cm) and Near (40 cm).
 
Note:
 
 • The room illuminance must be between 7.3 and 7.9 EV (or 400 to 600 lux) • Distance, HC-1 Chart luminance Acceptable EV Range 10.5-10.7 (or 180 to 210 cd/m²) • Guillon-Poling, Near Chart Luminance Acceptable EV Range 10.8-11.1 (or 220 to 280 cd/m²) • Do not use the Mesopic filter for Dim luminance (Dim luminance will be simulated by using the goggles). 	
4.12.	Lens Removal	Have the subject remove the study lenses. Temporarily store the worn lenses until Biomicroscopy has been completed. If no adverse event or PQC was recorded, the worn lenses may be discarded.	

FINAL EVALUATION

The final evaluation will ordinarily take place immediately following the last scheduled follow-up visit per the study protocol. It may also take place at any point the subject discontinues the study or is terminated from the study.

Clinical Study Protocol
Johnson & Johnson Vision Care, Inc.

Final Evaluation			
Step	Procedure	Details	
F.1	Final Exam Form	Indicate if the subject completed the study successfully. If subject discontinued from the study, indicate the reason.	
F.2	Biomicroscopy	FDA Slit Lamp Classification Scale will be used to grade the findings and determine eligibility. If the clearance of the fluorescein needs to be expedited, preservative-free rewetting drops or saline may be instilled.	
F.3	Subjective spherocylindrical Refraction	An optimal, binocular balanced distance spherocylindrical refraction will be performed. Record the refraction and distance visual acuity (OD, OS, OU) to the nearest letter.	
F.4	Exit Distance Visual Acuity	Record the distance Snellen visual acuity (OD, OS, OU) to the nearest letter, and the type of visual correction being worn (habitual lenses, distance spectacles or unaided).	

7.3. Unscheduled Visits

If, during the investigation, a subject requires an unscheduled visit to the clinical site, the following information will be collected at a minimum:

- Chief complaint prompting the visit. If the reason is an adverse event, the applicable eCRF for the adverse event must be completed and subject record completed as appropriate
- Date and time of the visit and all procedures completed at the unscheduled visit
- Review of adverse event and concomitant medications
- Documentation of any test article dispensed or collected from the subject, if applicable
- Slit lamp findings (using the Slit Lamp Classification Scale)

If the Investigator withdraws a subject from the study, the final study visit case report forms must be completed indicating the reason(s) why the subject was withdrawn. The subject record must be completed documenting the date and primary reason for withdrawal and the study CRA notified.

Any ocular and non-ocular Adverse Events that are ongoing at the time of the study visit will be followed by the Investigator, within licensure, until they have resolved, returned to pre-treatment status, stabilized, or been satisfactorily explained. If further treatment i.e., beyond licensure is required, the subject will be referred to the appropriate health care provider.

The following information will be collected during an unscheduled visit.

Clinical Study Protocol
Johnson & Johnson Vision Care, Inc.

Unscheduled Visit			
Step	Procedure	Details	
U.1	Reason for unscheduled visit	Indicate if the only reason for the visit is that the subject requires additional test articles. If the reason is other than resupply of previously dispensed lenses, specify the reason for the visit.	
U.2	Chief Complaints (if applicable)	Record the subject's chief complaints for reasons for the unscheduled visit.	
U.3	Adverse Events and Concomitant Medications Review (if applicable)	Review any changes to the subject's medical history or concomitant medications from the previous study visit. Record any changes, and any adverse events.	
U.4	Entrance VA (if applicable)	Record the distance Snellen visual acuity (OD, OS, OU) to the nearest letter, and the type of visual correction being worn (study lenses, habitual lenses, distance spectacles or unaided).	
U.5	Subjective Sphero-cylindrical Refraction (if applicable)	Perform bare-eye subjective sphero-cylindrical refraction with a phoropter (adopt the maximum plus to maximum visual acuity (MPMVA) approach and use the duo-chrome test for binocular balancing) and record the best corrected distance visual acuity to the nearest letter (OD, OS).	
U.6	Slit Lamp Biomicroscopy (if applicable)	FDA Slit Lamp Classification Scale will be used to grade the findings. If the clearance of the fluorescein needs to be expedited, preservative-free rewetting drops may be instilled.	
U.7	Dispensing (if applicable)	If the subject requires additional lenses to complete the wear period and is eligible to do so, provide additional lenses per the dispensing instructions given in the detailed study procedures.	
U.8	Toric Fit Evaluation (if applicable)	After lens settling, record: 
 • The rotational position to the nearest degree • Lens stability with blink • Lens stability with eye versions • Toric fit acceptable or unacceptable Toric lens fit will be unacceptable if lenses rotated more than 30 degrees, or lens stability is worse than 5 degrees movement	

Clinical Study Protocol
Johnson & Johnson Vision Care, Inc.

Unscheduled Visit			
Step	Procedure	Details	
		
with blink. If toric fit is unacceptable, remove, store, and label the lenses, and proceed to final evaluation.
	
U.9	Lens Fit Assessment (if applicable)	
Evaluate and grade lens centration, primary gaze movement, upgaze movement and tightness (push-up test).
 
 • The subject should not proceed to wear the lenses if any of the following is observed: • presence of limbal exposure (appearance of clear cornea) in any gaze • presence of edge lift • presence of unacceptable movement (excessive or insufficient) in all three movement categories (primary gaze, upgaze, and push-up). 
If either lens is deemed unacceptable, the subject will be discontinued from the study. Remove the lenses, perform a slit-lamp evaluation, and complete the Final Evaluation form.
	
U.10	Exit Visual Acuity (if applicable)	
Record the distance Snellen visual acuity (OD, OS, OU) to the nearest letter, and the type of visual correction being worn (study lenses, habitual lenses, distance spectacles or unaided).
	

7.4. Laboratory Procedures

None

8. SUBJECTS COMPLETION/WITHDRAWAL

8.1. Completion Criteria

Subjects are considered to have completed the study if they:

- provided informed consent.
- are eligible.
- completed all visits

Clinical Study Protocol

Johnson & Johnson Vision Care, Inc.

8.2. Withdrawal/Discontinuation from the Study

A subject will be withdrawn from the study for any of the following reasons:

- Subject death during the study period.
- Subject withdrawal of consent.
- Subject not compliant to protocol
- Subject lost to follow-up.
- Subject no longer meets eligibility criteria (e.g. the subject becomes pregnant).
- Subject develops significant or serious adverse events causing discontinuation of study lens wear.
- Subjects who have experienced a Corneal Infiltrative Event (CIE).
- Investigator's clinical judgment regarding the subject safety reasons (that it is in the best interest of the subject to stop treatment).
- Subject missed any study visit.
- Subject not compliant with study lens wear schedule.
- Subject not successfully dispensed due to lack of efficacy and safety including poor vision, poor comfort or unacceptable fit.

For discontinued subjects, the Investigator will:

- Complete the current visit (scheduled or unscheduled).
- Complete the Final Evaluation, indicating the reason that the subject was discontinued from the study.
- Record the spherocylindrical refraction with best corrected distance visual acuity.
- Collect used test article(s) (worn or brought to the visit) from the subject and discard them, unless otherwise stated in Section 7.2.
- Collect all unused test article(s) from the subject.
- Make arrangements for subject care, if needed, due to their study participation

An additional subject may be enrolled if a subject discontinues from the study prematurely.

In cases where a subject is lost to follow-up, every possible effort must be made to contact the subject and determine the reason for discontinuation/withdrawal. The measures taken to follow up must be documented including two written attempts and a certified letter (or equivalent) as the final attempt.

9. PRE-STUDY AND CONCOMITANT INTERVENTION/MEDICATION

Concomitant medications will be documented during screening and updated during the study. Disallowed medications and therapies are medications or therapies that contraindicate contact lens wear. See the Exclusion criteria for specific details.

9.1. Systemic Medications

Certain systemic medications are known to have a higher likelihood to interfere with contact lens wear, chiefly by disrupting the tear film. A summary of disallowed medications is shown

Clinical Study Protocol

Johnson & Johnson Vision Care, Inc.

in Table 4. Subjects with a history of taking these medications will be allowed to enroll only if:

- The medications have been taken on a continual or routine basis for at least 6 months and the subject has demonstrated successful contact lens wear during this time.

Or

- The subject previously used these medications on a temporary basis and has ceased that medication at least 1 week prior to signing the informed consent.

Table 4: Disallowed systemic medications

Class of Drug	Common Indication(s)	Common Examples
Anticholinergics	Irritable bowel syndrome, Parkinson's disease, peptic ulcer, cystitis, nasal congestion, cold symptoms, overactive bladder, COPD	Bentyl, Spiriva, Atrovent, Hyosyne, Levsin, Symax Fastab, Symax SL, Homax SL, Cogentin, Transderm Scop, etc.
Oral Phenothiazines	Antipsychotic disorders (schizophrenia, mania)	Compazine, Mellarill, Thorazine, Phenagran, etc.
Oral/Inhaled Corticosteroids	Arthritis, colitis, asthma, bronchitis, allergic or inflammatory conditions	Cortisone, Prednisone, Hydrocortisone, Medrol, Kenalog, Flonase etc.
Oral Retinoids	Seborrhea, acne	Isotretinoin, Acitretin, Alitretinoin, etc.
Oral Tetracycline	Urinary Tract Infection, acne, chlamydia, gonorrhea	Sumycin, Achromycin V, etc.

10. DEVIATIONS FROM THE PROTOCOL

Investigator will notify study sponsor upon identification of a protocol deviation. Protocol deviations must be reported to the sponsor within 24 hours after discovery of the protocol deviation. The Investigator will report deviations per IRB/IEC requirements. All deviations will be tracked, and corrective actions implemented as appropriate.

If it becomes necessary for the Investigator to implement a deviation in order to eliminate an immediate hazard to the trial subject, the Investigator may implement the deviation immediately without notification to the sponsor. Within 24 hours after the implemented deviation, the Investigator must notify and provide the rationale to the Sponsor and, as required, the IEC/IRB.

If the deviation potentially impacts the safety of patient or changes the technical integrity of the study, then it must be reported to IEC/IRB. This is a "Major Deviation". Deviations that contradict the information contained in the Informed Consent/Accent forms will be considered Major Deviations.

Clinical Study Protocol

Johnson & Johnson Vision Care, Inc.

Minor deviations have no substantive effect on patient safety or technical integrity of the study. They are often logistical in nature.

Protocol waivers are prohibited.

Table lists examples of deviations that will constitute major and minor protocol deviations for this study.

Table 5: Examples of major and minor protocol deviations

Deviation category	Major deviation	Minor deviation
Out-of-window visit	Visit attended 3 or more days out of visit window defined in study procedures	Visit attended 2 or fewer days out of visit window defined in study procedures
Insufficient wear of study lenses	Subject does not wear study lenses for at least 6 hours per day for 3 or more days out of any week through the dispensing period.	Subject does not wear study lenses for at least 6 hours per day for 2 days out of any week through the dispensing period.

11. STUDY TERMINATION

If more than 2 subjects in the investigational soft contact lens group develop serious expected (e.g., definite or probable MK) or unexpected device related adverse events, the study will be suspended. Upon review and consultation with IRB, DMC, and JJVC Safety Review committee, the study may be terminated. This potential stopping rule is established based on our trial involving approximately 200 subjects wearing the investigational soft contact lens for up to 3 years with an assumed MK rate that is below 0.2% per patient-year. The rate of 0.2% per patient year is the established rate for extended wear lenses in adults, which was requested by the FDA as a criterion for evaluating a contact lens for pediatric use in an FDA response to a pre-IDE submission. To be conservative, 200 independent patient years were used in the calculation. The probability of observing 2 cases or more incidents of MK is 0.061, and 3 cases or more incidents of MK is 0.007 (given an MK rate of 0.2% per patient year).

The occurrence of one or more Unanticipated Serious Adverse Device Effect (USADE), or any SAE where the relationship to study agent cannot be ruled out, may result in stopping further dispensing of test article. In the event of a USADE or SAE, the Sponsor may unmask the treatment regimen for the subject(s) and will discuss this with the Investigator before any further subjects are enrolled.

Clinical Study Protocol

Johnson & Johnson Vision Care, Inc.

The Sponsor will determine when a study will be stopped. The Principal Investigator always has the discretion to initiate stopping the study based on patient safety or if information indicates the study's results are compromised.

JJVC reserves the right to terminate the study at any time for any reason. Additionally, the IEC/IRB reserves the right to terminate the study if an unreasonable risk is determined. The study can be terminated by the Principal Investigator at the individual clinical site due to specific clinical observations, if in their opinion, after a discussion with JJVC, it is determined that it would be unwise to continue at the clinical site.

JJVC (and the IEC/IRB and DMC, if applicable) will evaluate all adverse events. If it is determined that an adverse event presents an unreasonable risk, the investigation, or that part of the investigation presenting the risk, will be terminated as soon as possible.

Should the study be terminated (either prematurely or as scheduled), the Investigator will notify the IEC/IRB and Regulatory Authority as required by local regulatory requirements.

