13. ADVERSE EVENTS

13.1. Definitions and Classifications

Adverse Event (AE) – An AE is “any untoward medical occurrence, unintended disease or injury, or untoward clinical signs (including abnormal laboratory findings) in subjects, users or other persons, whether or not related to the investigational medical device.”

Note: This definition includes events related to the investigational medical device or the comparator, and to the procedures involved. For users or other persons, this definition is restricted to events related to investigational medical devices.¹

An AE includes any condition (including a pre-existing condition) that:

1. Was not present prior to the study, but appeared or reappeared following initiation of the study.
2. Was present prior to the study but worsened during the study. This would include any condition resulting from concomitant illnesses, reactions to concomitant medications, or progression of disease states.

Note: Pregnancy must be documented as an adverse event and must be reported to the clinical monitor and to the Sponsor immediately upon learning of the event.

Serious Adverse Event (SAE) – An SAE is any adverse event that led to any of the following:

Clinical Study Protocol

Johnson & Johnson Vision Care, Inc.

- Death
- Serious deterioration in the health of the subject that resulted in any of the following:
- Life-threatening illness or injury
- Permanent or persistent impairment of a body structure or a body function
- Hospitalization or prolongation of patient hospitalization
- Medical or surgical intervention to prevent life-threatening illness or injury or permanent impairment to a body structure or a body function.
- Chronic disease
- Foetal distress, foetal death or a congenital physical or mental impairment of birth defect.

Diagnoses and conditions that are considered Ocular Serious Adverse Events include, but not limited to:

- Microbial Keratitis (MK)
- Iritis (including cells in the anterior chamber)
- Permanent decrease in best spectacle corrected visual acuity equivalent to 2 acuity lines or greater
- Central Corneal Opacity
- Central Corneal Neovascularization
- Uveitis
- Endophthalmitis
- Hypopyon
- Hyphemia
- Penetration of Bowman's Membrane
- Persistent Epithelial Defect
- Limbal cell Damage leading to Conjunctivalization

Significant Adverse Events – are defined as events that are symptomatic and warrant discontinuation (temporary or permanent) of the contact lens wear

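### Section 11 justifies its suspension threshold with microbial keratitis probabilities for 200 patient-years, but this trial has about 8.6; the same paragraph names a DMC that the trial does not have

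*Combined protocol and SAP*

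**What the plan says.** Section 11 has one rule that acts automatically at a stated count. If more than 2 subjects "develop serious expected (e.g., definite or probable MK) or unexpected device related adverse events, the study will be suspended". The rationale is that the rule is "based on our trial involving approximately 200 subjects wearing the investigational soft contact lens for up to 3 years", with an assumed MK rate below 0.2% per patient-year. Section 11 describes that rate as the established one for extended wear in adults, requested by the FDA as a criterion for a pediatric lens. On exposure it says: "To be conservative, 200 independent patient years were used in the calculation". It then reports 0.061 for 2 or more MK cases and 0.007 for 3 or more.

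After suspension, the next step is: "Upon review and consultation with IRB, DMC, and JJVC Safety Review committee, the study may be terminated". Section 16.4, on the DMC, reads not applicable.

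Section 11 also has provisions that do not depend on a count. A single unanticipated serious device effect, or a single SAE whose relationship cannot be ruled out, "may result in stopping further dispensing of test article". In that event the Sponsor may unmask "and will discuss this with the Investigator before any further subjects are enrolled". If an adverse event is judged an unreasonable risk, "the investigation, or that part of the investigation presenting the risk, will be terminated as soon as possible".

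The trial itself is described in the Synopsis and sections 3.2, 4.1 and 7.2 (step 1.36): about 90 enrolled with at least 80 to complete, ages 40 to 70, daily wear, and about five weeks on a marketed lens.

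**The concern.** The sample size, duration, wear mode behind the reference rate, and pediatric purpose in the rationale all differ from this trial. A count that suits one exposure need not suit another: with much less exposure, far fewer events are expected and each one carries more information. A sponsor or IRB reading section 11 would take 0.061 and 0.007 as the operating figures of this study's rule, when they belong to a design with about 23 times the exposure. For MK, the only event used to justify the count, the automatic rule would almost never act, even if the true rate were many times the benchmark. The DMC reference adds a smaller inconsistency, because the review sentence names a body that the trial does not have.

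**Working it through.** **Inputs**
- Threshold: 3 or more subjects (section 11).
- Rate: 0.2% per patient-year (section 11).
- Exposure in the stated calculation: 200 patient-years (section 11).
- This trial: about 90 subjects for about five weeks, taken as 35 days (Synopsis). The wear windows are 5–9 days and then 25–31 days, so 30 to 40 days in all. At least 80 subjects are to complete.

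**1. Reproduce the plan's figures.** Binomial with n = 200 and p = 0.002:
- P(2 or more) = 0.0614, stated as 0.061.
- P(3 or more) = 0.0078, stated as 0.007 (truncated rather than rounded).

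A Poisson with mean 200 × 0.002 = 0.4 gives 0.0616 and 0.0079. The arithmetic is sound for 200 patient-years.

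**2. Exposure in this trial.**
- Central: 90 × 35 / 365.25 = 8.62 patient-years.
- Low: 80 × 30 / 365.25 = 6.57.
- High: 90 × 40 / 365.25 = 9.86.
- Ratio: 200 / 8.62 = 23.2.

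The range is indicative and not a strict bound. The low end gives non-completers no exposure, and discontinued subjects may be replaced.

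**3. MK probabilities at the same 0.2%.** Poisson with mean 8.62 × 0.002 = 0.01725:

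| MK cases | This trial (range) | Section 11 |
|---|---|---|
| 1 or more | 0.0171 (0.0131–0.0195) | not given |
| 2 or more | 0.000147 (0.000086–0.000192) | 0.061 |
| 3 or more | 8.4e-7 (3.7e-7 to 1.26e-6) | 0.007 |

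**4. Sensitivity to a raised rate.** At ten times the benchmark (2% per patient-year), P(3 or more) is 0.00075 here, against 0.765 in 200 patient-years. For 3 or more cases to have probability 0.007 here, the Poisson mean must be 0.382, so the rate must be 0.382 / 8.62 = 4.4% per patient-year, or 22 times the benchmark.

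**5. What count would match, if a tail cutoff was used.** At 200 patient-years, 3 is the smallest count with tail probability below c for any c from 0.0078 to 0.0614. At 8.62 patient-years:
- c from 0.0171 to 0.0614 gives 1 case.
- c from 0.0078 to 0.0171 gives 2 cases.

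This does not hinge on the exact exposure. Even for 2 or more cases to have probability 0.007, the mean must be 0.1233, which is 0.1233 / 0.002 = 61.6 patient-years, about 7 times what this trial has.

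**6. The DMC.** The consultation sentence in section 11 names the DMC without qualification, and section 16.4 says not applicable. The qualifier that a DMC takes part only if applicable appears in a later section 11 sentence on evaluating adverse events, not in this one. The suspension sentence itself needs no committee.

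**The case against.** Several counter-arguments have force.

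- **How 3 was chosen is unknown.** Section 11 reports tail probabilities but does not say that they set the count. If 3 was a clinical choice and the probabilities are only descriptive, step 5 does not show that 3 is the wrong number. A reader might infer that it does; the documents do not support that. What stands regardless is that the printed probabilities do not describe this trial.
- **The rule covers more than MK.** Section 13.1 gives an open list ("Diagnoses and conditions that are considered Ocular Serious Adverse Events include, but not limited to"), and the rule also reaches unexpected device-related events. Nothing here shows that the whole rule is inert: the documents give no rate for the other events, so its overall behaviour cannot be computed.
- **Subjects are not unprotected after one MK case.** Serious events are reported within 24 hours (section 13.4.1), a subject whose event stops lens wear is withdrawn (section 8.2), and the single-event provisions of section 11 apply. A reader might conclude that nothing happens before the third case; the text says otherwise. But stopping dispensing is discretionary and mandatory termination needs a prior judgement, so the count rule remains the only automatic one.
- **The DMC slip does not disable the rule.** Suspension happens without it, and the IRB and the sponsor's safety review committee are named in the same sentence.
- **The 0.2% rate is itself an extended-wear benchmark.** That is right. No daily-wear rate is in the documents, so every figure built on 0.2% must be labelled an assumption.
- **MK is unlikely here.** At 0.2%, the chance of no case is about 98%. This limits the consequence but does not make the stated figures correct.

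**Conclusion.** The point holds for MK calibration and for the DMC reference. The stated 0.061 and 0.007 apply to about 23 times this trial's exposure; at the same rate the values are about 0.00015 and 8e-7. If a tail cutoff set the count at 3, that cutoff gives 1 or 2 MK cases here. The numbers rest on 90 subjects for 35 days, a constant rate, independent cases, and the plan's 0.2%, which is borrowed from another wear mode. That the rationale was carried over from another protocol is an inference; that it does not describe this study is plain from the text. The primary analysis is unaffected and the safety consequence is modest, given the single-event provisions. The section should still be corrected, because it gives the sponsor and IRB operating figures that are not this study's.

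**What to change.** Four wording changes in section 11:

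1. Replace the 200-subject, 3-year and pediatric rationale and its probabilities with this trial's exposure (about 90 subjects for about five weeks, about 8.6 patient-years) and the resulting figures: 0.017 for 1 or more MK cases, 0.00015 for 2 or more and 8e-7 for 3 or more. Label 0.2% per patient-year as an assumed extended-wear benchmark.
2. Add a separate, lower trigger for definite or probable MK, at 1 or 2 cases, and state the criterion. A 5% tail gives 1 case and a 1% tail gives 2. The choice is a clinical and sponsor judgement.
3. Leave the existing limb as it stands, at more than 2 subjects who "develop serious expected (e.g., definite or probable MK) or unexpected device related adverse events, the study will be suspended". Rewriting it as serious device-related events only could drop unexpected events that the present wording may count.
4. Delete the DMC from the consultation sentence, leaving the IRB and the sponsor's safety review committee.

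This needs no new committee, data or visits. The cost is a small chance of a needless temporary pause at 0.2% per patient-year: about 1.7% (1.3–2.0%) with a one-case MK trigger, or about 0.015% with a two-case trigger. If the sponsor prefers to keep 3 for MK on clinical grounds, changes 1 and 4 are still needed, and the text should say that the count was a clinical choice.
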